## Study Protocol and Statistical Analysis Plan

### Summary

The purpose of this pilot study is to assess obese clients for two phenotypes, those testing positive and those testing negative for Food Addiction (FA) (Yale Food Addiction Scale, YFAS) and determining the efficacy of four treatments: usual care (IC, dietary and physical activity instruction), individual motivational interviewing alone (MI), individual MI with pharmacotherapy (MI+P) for improving outcome measures within each phenotype, and pharmacological therapy (P).

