The prevalence of FA is estimated to be 25% in the population of urban adult women who have a BMI classification of overweight or obese. Using this prevalence along with a medium effect size, a statistical power analysis was performed for sample size estimation with G\*Power 3.1. The design is a stratified four-group design with a pre and post measurement. Stratification by obesity phenotype (positive or negative for FA) will occur first, followed by random assignment to one of four treatment groups [Information Control (dietary and physical activity instruction), MI alone(diet and physical activity instruction supported by MI), MI((diet and physical activity instruction supported by MI+P(Contrave)). Using an  $f = 0.25$ , an  $\alpha = .05$  and  $\text{power} = 0.95$ , the a priori F test, analysis of variance, omnibus, one-way model gives a projected sample size of 252. As a pilot study, this study is underpowered for statistical hypothesis testing, and analyses will focus on descriptive statistics, estimation of effect sizes, and hypothesis generation and a sample of 40 eligible patients will be enrolled (10 in each group). This meets the pilot study guideline of at least 10% of a fully powered trial and remains realistic in terms of time and cost (Hertzog, 2008) while allowing for 50% attrition. It is expected that 25% of the population will meet the criteria of FA and therefore will need to screen and consent a total of 160 participants to reach the 40 people positive for FA. No more than 160 subjects will be consented for the entire pilot study.

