#### Proposed methods/approach

Investigators propose assessing obese clients with the YFAS as part of their intake once they are referred to the Healthy Behaviors Clinic by Regional West physicians/practitioners. A nurse researcher with expertise in MI and a nurse practitioner will perform intake assessments, obtain consent and randomly assign participants in each phenotype (positive or negative for FA) to one of three treatment groups (usual care, individual MI alone, and individual MI with pharmacotherapy). Interventions will occur over 6 months. A clinical psychologist with expertise in the YFAS (University of Michigan) will serve as a consultant on this project and a registered dietitian (University of Nebraska Lincoln) will serve as a co-investigator.

Investigators expect that MI and MI+P and P will be more effective in improving outcome measures than IC. We also expect that response to the treatments will differ between the two obesity phenotypes (those testing positive and those testing negative for FA).

To determine if MI alone or MI+P or P is effective in treating obese patients with and without FA (based on the YFAS) as determined by :

- Higher MI confidence, importance and readiness to change scores
- Reduced intake of foods that are highly processed and high in fat and sugar (HPFS) and increased intake of complex carbohydrate foods(fresh fruits, vegetables, whole grains) and minimally processed proteins (nuts, fresh meats) (ASA24-2016® dietary recall)
- Improved biometric measures (BMI, body composition, waist circumference, and blood pressure)

-To determine whether the two obesity phenotypes (with and without FA) differ in their response to the four treatments.

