**Initial Screening for Eligibility (Suicidal Ideation, Pregnancy test (urine test), Lactation, Recruitment):**  
Participants will be recruited from obese patients referred to the Healthy Behaviors Clinic by Regional West Physicians. Nurse researchers who work at the Healthy Behaviors Clinic will inform potential participants about the study and, if they agree to participate, will consent them.

Both treatment groups, Those who test positive for and those who test negative for FA (food addiction) will be assigned to one of four treatment arms, IC, MI, MI+P and P. All will receive dietary and exercise information. After consenting, each participant will be administered the YFAS to determine their obesity phenotype (positive or negative for FA). Participants within each phenotype will be randomly assigned to one of the intervention (MI or MI+P, or P) or the IC information control (diet and physical activity instruction, which will be no less than current standard of care) treatment groups using a randomization schedule (assignments in numbered, sealed, opaque envelopes; one set for each phenotype) 1:1:1:1 ratio, provided by our statistician, [name]. Phenotype assessment and treatment assignment will continue until the sample size (n=10) is met for each phenotype-treatment group category. Those in the control group will be seen at the same time periods as each treatment group to maintain their interaction time with the clinic. They will receive diet and exercise instruction at each time point.

**Intervention Conditions (MI, MI+P):** MI is theorized to decrease a patient's ambivalence and increase his/her perceived behavioral control (self-efficacy) for limiting HPFS and increasing CC intake by emphasizing personal choice and control in decision-making and by affirming the patient's self-management ability. Interventionist nurses will deliver MI sessions following data collection at baseline, 1, 2, 3, and 4 weeks and 2, 3, 4, 5, and 6 months to promote sustained behavioral change. A written MI algorithm will be used to ensure uniform implementation of the intervention.

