#### Statistical Methods to Analyze Data

Missing data will be evaluated. For summated scales on which fewer than 20% of an individuals responses are missing, the individuals mean on the remaining items may be substituted, as appropriate. For analyses requiring complete data, imputation of missing values using the EM algorithm or multiple imputations will be considered, as appropriate. Scoring algorithms for each instrument will be used per the published use manual. Each statistical test will be conducted at  $p=.05$  level. Data will be analyzed using descriptives (means, medians, standard deviations of scores), independent t-tests, correlation coefficients and analysis of variance. In Aim 1, ANOVA will be used to assess differences between the three treatment groups on the YFAS to determined changes in MI confidence, importance and readiness to change scores as well as ASA24-2016® dietary recall and biometric measures. Correlational analysis will be used to explore the relationships between ASA24-2016® dietary recall and biometric measures. In Aim 2 independent t-test will be used to determine if the positive and negative YFAS groups differ across treatment responses.

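### Aim 1 asks about efficacy within each food-addiction phenotype, but its ANOVA names only treatment group and so yields no arm-versus-control effect in either phenotype

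*Combined protocol and SAP*

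**What the plan says.** The Summary gives the purpose as determining the efficacy of four treatments "for improving outcome measures within each phenotype". The objectives under Proposed methods/approach repeat this, asking whether the active treatments are effective in patients both with and without FA. The same section adds: "We also expect that response to the treatments will differ between the two obesity phenotypes".

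The design follows that question. The sample-size paragraph under Contribution to Science states: "Stratification by obesity phenotype (positive or negative for FA) will occur first, followed by random assignment to one of four treatment groups". The assignment paragraph under Initial Screening for Eligibility says "Participants within each phenotype will be randomly assigned", using "assignments in numbered, sealed, opaque envelopes; one set for each phenotype", in a 1:1:1:1 ratio, until 10 are reached in each phenotype-by-treatment category.

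The analysis does not follow it as clearly. Statistical Methods to Analyze Data says "In Aim 1, ANOVA will be used to assess differences between the three treatment groups". The sentence then mentions the YFAS in a way that is hard to parse, and lists the outcomes. It names no phenotype term, interaction or within-phenotype analysis. Phenotype enters only in Aim 2, as an independent t-test of FA-positive against FA-negative participants.

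**The concern.** The effects the trial was set up to estimate are each arm minus IC among FA-positive patients, and the same among FA-negative patients. A one-factor ANOVA across treatment groups returns neither. Its contrast is a weighted average of the two, and the investigators themselves expect the two to differ. If they do, the reported effect size belongs to neither phenotype.

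This matters more because the study is a pilot whose declared output is effect-size estimation and hypothesis generation. A later phenotype-targeted trial would need the phenotype-specific numbers. Omitting a stratification factor can also cost precision.

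**Working it through.** **The plan's own figure.** The projected 252 comes from a one-way omnibus ANOVA with f = 0.25, α = 0.05 and power 0.95. Using the noncentral F with λ = f²N and df = k − 1 and N − k:

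- k = 3 groups: N = 252, power 0.951. This reproduces the figure.
- k = 4 groups: N = 280. Power at 252 is 0.926.

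So the sizing model also has treatment as its only factor. The three-versus-four-group mismatch is a separate matter.

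**What each planned analysis estimates.** Let m(a,+) and m(a,−) be the mean responses in arm a for FA-positive and FA-negative patients, and w the FA-positive share, taken as equal across arms.

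- Wanted: d₊ = m(a,+) − m(IC,+) and d₋ = m(a,−) − m(IC,−).
- Aim 1 as written: w·d₊ + (1 − w)·d₋.
- Aim 2 t-test: m(+) − m(−), overall or within an arm. This compares phenotypes, not an arm with IC.

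If the Aim 2 test were run arm by arm and cell means were printed, a reader could subtract them by hand. The plan does not make that an output and gives it no interval.

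**How far the average can sit from both effects.** The effects below are assumed, in SD units, because the documents give none by phenotype. Ten per cell implies w = 0.5.

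- d₊ = 0.8, d₋ = 0.2: 0.5 × 0.8 + 0.5 × 0.2 = 0.50.
- d₊ = 0.5, d₋ = −0.5: 0.5 × 0.5 + 0.5 × (−0.5) = 0.
- d₊ = d₋: the average equals both, and nothing is lost on this count.

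Whenever the effects differ, any w strictly between 0 and 1 gives a value strictly between them. The point therefore does not depend on a 50:50 mix.

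**Precision lost by omitting the stratum.** If phenotype explains a share R² of outcome variance, residual variance is multiplied by 1/(1 − R²) and interval width by its square root. R² is assumed.

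| R² | Variance factor | Width factor |
|---|---|---|
| 0.05 | 1/0.95 = 1.05 | 1.026 |
| 0.20 | 1/0.80 = 1.25 | 1.118 |

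A simulation (40,000 runs, 4 arms × 2 phenotypes × 10, no treatment effect) shows the direction. For assumed phenotype mean differences of 0.5, 0.8 and 1.0 SD, the variance factor 1 + D²/4 is 1.06, 1.16 and 1.25. The nominal 5% one-way test rejects about 4.1%, 2.9% and 2.1% of the time. With the phenotype cells in the model it stays near 5%.

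**Precision of the estimates that are wanted.** The half-width of a 95% CI for one arm minus IC within a phenotype, with residual variance from all eight cells, is t(0.975, 8n − 8) × √(2/n):

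- n = 10 per cell, 72 df: 1.993 × 0.447 = 0.89 SD.
- n = 5 per cell, 32 df: 2.037 × 0.632 = 1.29 SD.

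For comparison, the contrast averaged over phenotypes at 20 per arm (76 df) has half-width 1.992 × √(2/20) = 0.63 SD.

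**Which n applies.** The assignment paragraph implies 8 × 10 = 80 participants, and 50% attrition leaves 5 per cell. The sample-size paragraph says 40 are enrolled, 10 in each group, and also refers to reaching 40 FA-positive people. If 40 were the total, spread evenly, 40/8 = 5 per cell would be the number before attrition.

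**The case against.** The strongest reply is that pooling is inferred from silence. The plan never says the phenotypes are combined. The mention of the YFAS in the Aim 1 sentence may be a clumsy attempt to bring phenotype in, since the same section uses YFAS-positive and YFAS-negative as its phenotype labels. That stands as a limit on the claim: treatment-only is the plain reading, not a stated intention. If a within-phenotype analysis was meant, the same wording change is needed.

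A second reply is that this is a descriptive pilot and that within-phenotype intervals of 0.9 to 1.3 SD settle little. The imprecision is real. But effect-size estimation is the declared purpose, and a wide interval on the intended quantity is more useful than a narrower one on a different quantity. Nor is it fair to say that the question is wholly unanswered, because the listed means, medians and SDs could be tabulated by cell.

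Three stronger readings are tempting, and the documents do not support them:

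- **The average is wrong because it weights phenotypes 50:50 when the clinic population is 25:75.** No section sets a population-average effect as a target. The 25% is taken from urban women with overweight or obesity, and the Background gives nearly 20% among obese persons. The 50:50 mix holds only under the 10-per-cell statement, and attrition could shift it.
- **Omitting the stratum necessarily widens the error bars.** It does so only if phenotype predicts the outcome, and no figure for that is given.
- **Omitting the stratum produces false positives.** The simulation shows the reverse.

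**Conclusion.** The point holds as a mismatch between question and analysis. The Summary, the objectives and the stratified randomisation all concern treatment effects by phenotype, and no analysis specified for Aim 1 or Aim 2 delivers an arm-versus-IC effect in either one. This rests on the plain reading of an unclear sentence.

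Two consequences are conditional. The average misdescribes both phenotypes only if their effects differ, which the protocol expects. Intervals are too wide only if phenotype predicts outcome, and then modestly: about 2.5-12% for an assumed 5-20% of variance explained, in the conservative direction. The harm is to the effect sizes the pilot reports, not to error control. The change should be made, but the study does not fail without it.

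**What to change.** Rewrite Aim 1 as an arm-by-phenotype model, with four arms, two phenotypes, their interaction and a common residual variance. Report each arm minus IC with a 95% CI, separately for FA-positive and FA-negative participants. If an overall effect is also quoted, keep phenotype in the model and state the phenotype mix it averages over. Clarify what the mention of the YFAS in the Aim 1 sentence means, and correct the group count to match the four-arm design.

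The cost is SAP wording, with no new data or visits. The price in the results is visible imprecision: about ±0.9 SD at 10 per cell and ±1.3 SD at 5. Present these as estimates rather than tests. At f = 0.25 the interaction test would have power of about 0.42 with 80 participants and 0.21 with 40. Reconcile the enrolment totals in the sample-size and assignment paragraphs so that the expected precision can be stated in advance.

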Waist circumference: We will use the average of 2 measurements (cm) performed with the patient standing erect with their arms at their sides. Waist circumference will be measured at the uppermost lateral border of the right ilium at the end of normal expiration using an inelastic tape measure positioned around the trunk parallel to the floor. This measure is included because it is a better indicator of body fat and, therefore, health risk than

BMI: In addition, results of a recent study in this population demonstrated that waist circumference has potential as a means of identifying patients with or at risk for obesity and hypertension.

Blood Pressure: We will use the average of 2 blood pressure measurements performed using an Omron HEM- 907 automatic blood pressure monitor. The measurements will be performed while the patient is quiet and still using the appropriate sized cuff placed snugly around the upper arm approximately 2 to 3 cm above the antecubital fossa with the mark on the cuff aligned with the artery.

Determinants of Change Measures: MI Algorithm Questions: These reflect the PCBT determinants of behavior change (the patients perceptions toward limiting HPFS/increasing CC intake). They assess patient attitudes/beliefs (importance score), perceived norms (perceived barriers), and perceived behavioral control/self-efficacy (confidence score). These measures will be recorded by the interventionist nurses during each MI session for their assigned patients.

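### Aim 2 asks whether food-addiction phenotype modifies treatment response, but the planned t-test of FA-positive versus FA-negative cannot separate that from prognosis

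*Combined protocol and SAP*

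**What the plan says.** Under Proposed methods/approach, the second objective reads: "To determine whether the two obesity phenotypes (with and without FA) differ in their response to the four treatments". The same section states the matching hypothesis: "We also expect that response to the treatments will differ between the two obesity phenotypes". The aims are not numbered there; Aim 2 is identified by matching this objective to the analysis section.

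The design supports the question. Patients are stratified by FA status and randomised 1:1:1:1 within each stratum to IC, motivational interviewing (MI), MI with pharmacotherapy (MI+P) or pharmacotherapy alone (P). On size, the Initial Screening section says: "Phenotype assessment and treatment assignment will continue until the sample size (n=10) is met for each phenotype-treatment group category".

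Statistical Methods to Analyze Data gives Aim 2 one sentence: "In Aim 2 independent t-test will be used to determine if the positive and negative YFAS groups differ across treatment responses". Each test is at the .05 level. Analysis of variance is assigned to the other aim: "In Aim 1, ANOVA will be used to assess differences between the three treatment groups on the YFAS". Phenotype is not named as a factor there. No section mentions an interaction, a factorial model, or a comparison of arm effects between phenotypes.

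The sample-size paragraph sets the status of all this: "this study is underpowered for statistical hypothesis testing, and analyses will focus on descriptive statistics, estimation of effect sizes, and hypothesis generation".

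**The concern.** A difference in response to treatment is a difference between treatment effects: (active minus IC in FA-positive) minus (active minus IC in FA-negative). A two-sample comparison of the phenotypes is not that quantity. FA status is a patient characteristic, and nothing ensures that the two groups would change alike under the same care.

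The wording allows two readings of the t-test: one test pooled over arms, or a separate test in each arm. Neither uses IC as the reference. Analysing change scores does not help: that removes a difference in baseline level, but not a difference in change that would appear in every arm.

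At stake is what the pilot delivers. The protocol expects it to help identify better targeted approaches for each phenotype. If a prognostic gap is reported as a differential response, the next trial inherits a targeting hypothesis with no support.

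**Working it through.** **The plan's own figure.** The projected 252 comes from a one-way omnibus F test with f = 0.25, alpha .05 and power 0.95. With noncentrality N·f² = 252 × 0.0625 = 15.75, it reproduces for three groups (power 0.951). For four groups the balanced N is 280, and 252 gives power 0.926. Either way it is a one-way calculation, so it does not address the interaction.

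**What each analysis estimates.** Let δ be the FA-positive minus FA-negative difference in mean change under IC. Let γ be the extra difference in an active arm, so γ is the interaction contrast against IC.
- Phenotype gap within an active arm: δ + γ for that arm. Within IC: δ.
- Pooled gap with equal cells: δ + (γ_MI + γ_MI+P + γ_P)/4.
- Quantity the objective needs: each γ.

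The pooled test can be significant with every γ at zero, and can miss γ's that cancel. A within-arm test responds to γ but cannot separate it from δ.

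**Inputs for the size.** From the documents: four arms, two phenotypes, 10 per cell (2 × 4 × 10 = 80 patients), two-sided .05, and a 50% attrition allowance, which leaves 5 per cell. Assumed: SD of change 1, equal cells, and these effects:
- (a) Prognosis only: δ = 0.6, all γ = 0.
- (b) Opposing effects: MI helps only FA-negative and P helps only FA-positive, each by 1 SD. So δ = 0, γ_MI = −1, γ_P = +1, γ_MI+P = 0.
- (c) Same direction: δ = 0, γ = 1 in all three active arms.
- (d) No effect of any kind.

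**Formulas.** Within-arm t-test: noncentrality d·√(n/2) on 2n − 2 df. At d = 0.6 and n = 10 its power is 0.246, so at least one of four is 1 − (1 − 0.246)⁴ = 0.68. Pooled t-test in (a): the same formula with 4n per phenotype, giving 0.755. Interaction F: 3 and 8(n − 1) df, with noncentrality n times the sum of squared interaction residuals. In (b) that is 10 × (4 × 0.5²) = 10, or f = √(10/80) = 0.354. Pooled results in (b) and (c), and at least one within-arm result in (c), are from 40,000 simulated trials.

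Proportion of trials significant:

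| Scenario | n per cell | Pooled t | At least one of four within-arm t | Interaction F |
|---|---|---|---|---|
| (a) prognosis only | 10 | 75% | 68% | 5% |
| (a) | 5 | 46% | 44% | 5% |
| (b) opposing effects | 10 | 3% | 83% | 74% |
| (b) | 5 | 3% | 54% | 39% |
| (c) same direction | 10 | 90% | 92% | 32% |
| (c) | 5 | 60% | 65% | 17% |
| (d) nothing | 10 or 5 | 5% | 19% | 5% |

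The 19% in (d) is 1 − 0.95⁴ = 0.185. The pooled test falls below 5% in (b) because differences between arms inflate its SD.

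**Precision of the right estimate.** One interaction contrast combines four cell means, so its standard error is √(4/n). The 95% half-width is t(.975, 8(n − 1))·√(4/n):
- n = 10: 1.993 × 0.632 = 1.26 SD.
- n = 5: 2.037 × 0.894 = 1.82 SD.

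At the plan's f = 0.25, the interaction F has power 42% with 80 analysed and 21% with 40.

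**The case against.** **The objective can be read as simple effects.** IC is one of the four treatments, so the question could be whether the phenotypes differ on each treatment, and within-arm t-tests address that. If all four were reported side by side, a reader could see whether the gap already exists in IC. This shows that the wording is loose, but it does not rescue the analysis. The plan does not say that results will be shown by arm and phenotype, and it plans no estimate or interval for the difference between arms. A gap of the same size in every arm would still be read as differential response.

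**The Aim 1 ANOVA sentence might conceal phenotype as a factor.** Its wording is unclear, but it speaks of three treatment groups, names no phenotype factor and no interaction, and is attached to the other aim.

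**The pooled test does not always miss a real difference.** This stands. In scenario (c) it rejects more often than the interaction F test (90% against 32% at 10 per cell). Missing a true interaction needs effects that nearly cancel. The general weakness is specificity: a rejection does not say which of δ or γ caused it.

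**The basis for 5 per cell.** The sample-size paragraph says "a sample of 40 eligible patients will be enrolled (10 in each group"), but goes on to speak of screening until 40 FA-positive patients are reached. So 40 may be one stratum, which agrees with 10 per cell. The 5-per-cell figures then rest on the 50% attrition allowance alone, which is enough.

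**It is a pilot, and the replacement is imprecise.** Both are true. They limit how much any Aim 2 result can decide, but a pilot meant to estimate effect sizes still has to estimate the relevant one.

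**Conclusion.** The concern holds. On either reading, the planned t-test does not estimate the quantity that the second objective asks for, and no other part of the plan does. That conclusion follows from the algebra and does not depend on assumed effects. The percentages do: they assume unit SD, equal cells and illustrative effects that are not in the documents. With a 0.6 SD prognostic gap and no differential response, the planned test would point to a phenotype difference in 68% to 75% of trials at 10 per cell and 44% to 46% at 5 per cell, depending on the reading.

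This should be fixed, but it does not threaten a confirmatory conclusion, because the study disclaims one. The harm is a mislabelled effect size carried into the next trial.

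**What to change.** Replace the Aim 2 sentence with text such as: *For each dietary and biometric outcome, a linear model will include arm (four levels), phenotype and the arm-by-phenotype interaction, preferably adjusted for the baseline value. For each active arm versus IC, the difference in effect between FA-positive and FA-negative patients will be reported with a 95% confidence interval as an exploratory estimate. Any FA-positive versus FA-negative comparison, pooled or within an arm, will be labelled prognostic only.*

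The MI importance, confidence and readiness scores need separate handling. Under Data Collection, of the MI algorithm questions: "These measures will be recorded by the interventionist nurses during each MI session for their assigned patients". IC and P therefore have no planned values. Either limit the contrast for these scores to MI+P versus MI, compared between phenotypes, or record the scores in IC and P as well.

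The cost is SAP wording and one model per outcome. No extra patients are needed, and no new data for the dietary and biometric outcomes. Recording the MI scores in IC and P, if chosen, adds a few questions per visit. The real downside is imprecision: with half-widths of about 1.3 to 1.8 SD, this pilot can rule out only very large interactions, and the report should say so.
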